### **Handling of missing items for scales**

Because the ICC computation requires each item in its calculation, no imputation will occur in ICC analyses. If any of the individual items for any scale are missing or unknown, the total score for that scale for that visit will be considered missing.

Whether virtual administration of the clinical assessments will result in more missing item scores relative to the on-site assessment is also of interest. To address this question, the number of missing items across the administration of each of the clinical scales will summarized by modality.

For the MMRM objective in Part A and all analyses in Part B related to ADAS-Cog13 and ADCS-ADL, if a limited number of individual test items are missing, imputation using prorating will be implemented to obtain a total score. Details of this prorating and the circumstances in which it will be used are included in the SAP.

Whether virtual administration of the clinical assessments will result in more missing item scores relative to the on-site assessment is also of interest. To address this question, the number of missing items across the administration of each of the clinical scales will summarized by modality.

#### **9.4.2. Primary Endpoint(s)**

##### **Part A**

The primary objective for Part A of this study is to evaluate the reliability of VTC compared with on-site administered cognitive and functional measures. This will be assessed by estimating the ICC and the associated 95% confidence interval for the first pair of observations from participants and comparing the lower bound of the confidence interval to 0.70, the ICC cut-off for acceptable reliability.

Using the guidelines and notation for defining ICCs published by McGraw and Wong (1996), the ICC of primary interest for this study is a 2-way mixed model, interaction absent, with single measurements from each modality on participants, looking at absolute agreement – ICC(A,1). In the present study, the ‘raters’ are the 2 modalities by which the clinical scales are assessed, on-site and VTC. As we are interested in comparing these specific modalities, modality is considered a fixed effect.

An ANOVA model will be fit to the data with fixed effects of modality, time effect, age, years of education, and presence/absence of anti-dementia drugs. To estimate the ICC and the associated confidence interval, the appropriate mean squares from this model will be used for these estimates. Refer to the SAP for more details.

## Part B

The primary objective for Part B of the study is to characterize the safety and tolerability of donanemab. For Part B of the study, safety will be assessed by summarizing spontaneously reported AEs (including infusion-related reactions), laboratory analytes, vital signs and body weight measurements, ECGs, physical and neurological examinations, MRI scans, and C-SSRS assessments.

### 9.4.3. Secondary Endpoint(s)

To assess the effect of donanemab on clinical progression in participants with symptomatic AD, MMRMs will be fit to the Part B data up to Week 72 for ADAS-Cog13, ADCS-ADL, iADRS, MMSE, and CDR-SB. The models will include terms for visit, age, years of education, and presence/absence of anti-dementia drugs. Visit will be considered a categorical variable.

Observed case analyses will also be conducted for each scale. Additionally, if participant numbers are adequate, AD progression from these models can be compared to anticipated progression had the patient remained untreated. Details of such a comparison are contained in the SAP.

Change from baseline in brain amyloid deposition at Week 36 and Week 72 of Part B will be assessed using an MMRM. The model will include terms for visit, age, years of education, and presence/absence of anti-dementia drugs. Visit will be considered a categorical variable. An observed case analysis will also be conducted.

Change from baseline in brain region volumes at Week 72 for Part B will be assessed using an ANCOVA model. The model will include terms for age, years of education, and presence/absence of anti-dementia drugs. An observed case analysis will also be conducted. The brain regions of interest will be defined in the SAP.

PK analyses will be defined by the PK scientist and will be specified in the PK analysis plan.

Categorical displays of ADAs against donanemab and neutralizing antibodies will be presented.

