### 3. Objectives and Endpoints

Objectives	Endpoints
Primary	
Part A To evaluate the reliability of VTC compared with on-site administered cognitive and functional measures	The intraclass correlation between VTC and on-site assessment for PAIR 1 for 
 
• ADAS-Cog13
 
• ADCS-ADL
 
• MMSE
 
• CDR-SB
 

Part B To evaluate safety and tolerability of donanemab	Standard safety assessments in Part B: 
 
• Spontaneously reported AEs
 
• Clinical laboratory tests
 
• Vital sign and body weight measurements
 
• 12-lead ECGs
 
• Physical and neurological examinations
 
 MRI (ARIA and emergent radiological findings) Infusion-related reactions C-SSRS
Secondary	
To assess the effect of donanemab on clinical progression in participants with symptomatic AD	Change from baseline up to Week 72 as measured in Part B by: 
 
• MMSE score
 
• ADAS-Cog13 score
 
• iADRS score
 
• ADCS-iADL score
 
• CDR-SB
 

To assess the effect of donanemab on brain amyloid deposition	Change in brain amyloid plaque deposition from baseline at Week 36 of Part B as measured by florbetapir F 18 PET scan
To assess the effect of donanemab on brain region volumes	Change in volumetric MRI measures from baseline to Week 72 in Part B
To assess peripheral PK and presence of anti-donanemab antibodies	PK of donanemab in Part B. ADAs against donanemab in Part B including 
 
• treatment-emergent ADAs
 
• neutralizing antibodies
 

Tertiary/Exploratory	

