#### **8.1.1.5. ADCS-ADL**

The ADCS-ADL is a 23-item inventory developed as a rater-administered questionnaire that is to be answered by the participants study partner (Galasko et al. 1997, 2004).

For each of the specific items, the study partner is first asked if the participant attempted the ADL during the past 4 weeks. If the participant did attempt the ADL, the study partner is asked to rate the performance level based on a set of performance descriptions. Scores for each item and the overall score for the tool are calculated. The range for the total ADCS-ADL score is 0 to 78, with lower scores indicating greater level of impairment (Galasko et al. 1997, 2004).

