7.5. Efficacy Scales

Longitudinal assessment across scheduled visits will be summarized for Part B participants for ADAS-Cog₁₃, ADCS-iADL, iADRS Total Score, CDR Sum of Boxes, and MMSE Total Score.

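### Protocol 9.4.3 models ADCS-ADL in Part B, but the secondary endpoint is ADCS-iADL, for which neither document specifies a Part B model

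*Protocol*

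**What the plan says.** The clinical secondary endpoints for Part B are introduced in Protocol Section 3 as "Change from baseline up to Week 72 as measured in Part B by" five scores: MMSE, ADAS-Cog13, iADRS, ADCS-iADL and CDR-SB. The functional entry reads "ADCS-iADL score". The synopsis and SAP Table AACH.4.1 give the same five.

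For the analysis, Protocol 9.4.3 says that "MMRMs will be fit to the Part B data up to Week 72", and its list is ADAS-Cog13 followed by "ADCS-ADL, iADRS, MMSE, and CDR-SB". ADCS-iADL is not in it. The missing-items rule in Protocol 9.4.1 allows prorating for the Part A MMRM and for "all analyses in Part B related to ADAS-Cog"13 and ADCS-ADL; it does not name ADCS-iADL either.

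SAP 7.5 is the SAP's only text on Part B efficacy scales. It states "Longitudinal assessment across scheduled visits will be summarized for Part B participants", and its list is ADAS-Cog13 followed by "ADCS-iADL, iADRS Total Score, CDR Sum of Boxes, and MMSE Total Score". It names ADCS-iADL and not ADCS-ADL, and gives no model.

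**The concern.** An endpoint should be tied to an analysis of that same variable. Here the endpoint tables say one thing and the protocol's model list another. A programmer working from 9.4.3 would build the Week 72 functional model on the full inventory total. One working from SAP 7.5 would tabulate the instrumental score and fit nothing. Neither would produce a model-based Week 72 estimate for ADCS-iADL.

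Two further readings depend on the choice:

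- Protocol 8.1.1.4 builds iADRS from ADAS-Cog13 and ADCS-iADL. Under 9.4.3 the composite and its cognitive component are modelled, but the ADL model beside them is for a score that is not the composite's other component.
- Protocol 9.4.3 allows progression from these models to be compared with anticipated untreated progression. The untreated display that the SAP does describe, in 8.6, uses ADCS-iADL. A comparison of the 9.4.3 functional model with it would not be like for like.

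**Working it through.** The plan states no figure on this point, and no sample size, power or alpha depends on it. The only power figure, about 81% in Protocol 9.2, is for the Part A ICC on ADAS-Cog13. The check is therefore a comparison of texts.

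**Step 1. Which ADL score is named for Part B, and for what purpose?**

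| Place | Score named | Role |
|---|---|---|
| Protocol synopsis | ADCS-iADL | secondary endpoint |
| Protocol Section 3 | ADCS-iADL | secondary endpoint |
| SAP Table AACH.4.1 | ADCS-iADL | secondary endpoint |
| Protocol 9.4.3 | ADCS-ADL | MMRM and observed-case analysis |
| Protocol 9.4.1, missing items | ADCS-ADL | prorating rule |
| SAP 7.5 | ADCS-iADL | summary by visit |

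The endpoint is ADCS-iADL in 3 of 3 places. Of the five scores in the 9.4.3 list, four match the endpoint list. Part B models specified across both documents: none for ADCS-iADL, one for ADCS-ADL.

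**Step 2. Could the two names mean the same score?** The protocol does not use them that way. Section 8.1.1.5 describes ADCS-ADL as a 23-item inventory and states: "The range for the total ADCS-ADL score is 0 to 78". Section 8.1.1.4 derives iADRS from ADCS-iADL while saying that ADCS-ADL is what is administered. Section 9.4.1 treats ADCS-iADL as a score in its own right, whose absence makes iADRS missing. Section 3 uses ADCS-ADL for Part A and ADCS-iADL for Parts B and C.

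**Step 3. Does the SAP replace 9.4.3?** Protocol 9.4.1 lets the SAP change analysis methods without an amendment when no principal feature changes, but requires the change and its justification to be described in the SAP and the clinical study report. SAP 7.5 gives no justification for dropping the MMRM. The SAP revision history mentions only the Part C analyses and the feeder studies. On the text, 7.5 is not a documented replacement.

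**Step 4. Can the size be computed?** Assume that ADCS-iADL is the unweighted sum of some of the ADCS-ADL items. Then

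change in ADCS-ADL = change in ADCS-iADL + change in the remaining items,

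and the two mean changes differ by the mean change in the remaining items. The documents give neither the ADCS-iADL item set nor its range, and no expected change for either part. The difference could be zero or not; the documents do not say.

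**The case against.** The strongest reply is that the SAP already has the right variable. SAP 7.5 lists ADCS-iADL for Part B and omits ADCS-ADL, and the protocol makes the SAP the more detailed description. This stands in part. A reader might infer that ADCS-iADL goes unanalysed, or that the trial will report ADCS-ADL in its place. The documents do not support that: ADCS-iADL receives a summary, and under the SAP alone ADCS-ADL would not be analysed in Part B. The substitution lies in the protocol text.

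Second, the SAP's lack of a model is not specific to this score. Section 7.5 specifies no MMRM for any of the five scales. That is a separate gap, and correcting the name in 9.4.3 would not close it.

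Third, a reader might infer that 9.4.3 leaves function without a proper model, or that the composite becomes uninterpretable. Neither follows. CDR-SB, described in 8.1.1.1 as covering both cognition and function, is in the list, and so is iADRS, which contains ADCS-iADL. SAP 7.5 also summarises ADCS-iADL beside iADRS and ADAS-Cog13.

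Fourth, the prorating sentence can be read as already covering ADCS-iADL, since that score comes from the administered ADCS-ADL. That is possible, but the rule speaks of obtaining a total score and leaves the details to the SAP, whose Part B section gives none.

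Finally, it is tempting to say that the 9.4.3 model would overstate decline on the endpoint by some percentage. That would require an assumed decline on the endpoint and on the remaining items, and the documents supply neither.

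**Conclusion.** The mismatch is real. As written, the protocol specifies a Week 72 model for a score that is not a Part B endpoint, and neither document specifies one for the score that is. A drafting slip is the likely explanation, since the other four names agree.

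The consequence is modest. It concerns one secondary endpoint in a single-arm, open-label part whose primary objective is safety and for which Protocol 9.1 states no hypotheses. No error rate or sample-size claim is affected. The numerical effect on the functional result is unknown from the documents. The conclusion rests on the comparison of lists and on the protocol's own separate use of the two names, not on any assumed size of difference. It should be corrected before the Part B analysis, but it is not critical.

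**What to change.** - **Protocol 9.4.3:** replace ADCS-ADL with ADCS-iADL in the list of Part B MMRMs. The ADCS-ADL total may be kept as a labelled supportive analysis.
- **Protocol 9.4.1, missing items:** keep ADCS-ADL for the Part A MMRM and add ADCS-iADL for Part B. A plain swap would be wrong, because the same sentence governs Part A, where ADCS-ADL is the stated measure.
- **SAP 7.5:** state that the 9.4.3 MMRM applies to ADCS-iADL and the other listed scales. If a summary is meant to replace it, say so and give the reason, as Protocol 9.4.1 requires.

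The cost is minor text edits and one model pointed at a different variable. ADCS-iADL comes from the scale already administered, so no new data are needed, and the Part A analyses are unchanged.

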Visit Number	UP b	1	2	3	4	5	6	7	8	9	10	11 c	12 c	13 c	14 c	15	801 d	802 d	UV	ED	ED only if participant has completed V1 and received IP in Part B.
Weeks Relative to Baseline (V1)		0	4	8	12	16	20	24	28	32	36	40	44	48	60	72	84	96	997		Procedures for some visits may take more than 1 day.
Visit Interval Tolerance (days)		—	-7 to +10	±7	±7	±7	±7	±7	±7	±7	±7	±7	±7	±7	±7	±7	±7	±7			
12-lead ECG (central or local)		X			X			X			X			X	X				X		Perform prior to administration of IP, when appropriate. ECG at V14 not required for participants who completed dosing at V10.

		Part B: Open-Label															Part B: Follow-Up, UV, ED				Comments		
		Visit Number	UP b	1	2	3	4	5	6	7	8	9	10	11 c	12 c	13 c	14 c	15	801 d	802 d	UV	ED	
Weeks Relative to Baseline (V1)		0		4	8	12	16	20	24	28	32	36	40	44	48	60	72	84	96	997			Procedures for some visits may take more than 1 day.
Visit Interval Tolerance (days)		—		-7 to +10	±7	±7	±7	±7	±7	±7	±7	±7	±7	±7	±7	±7	±7	±7	±7	±7			
PET Scans and MRI																							Perform prior to V1 at UP if last recorded MRI from originating study occurred >12 months before V1.
MRI			X		X		X					X					X				X		MRI at V2 is to be performed and reviewed prior to V2 infusion and may occur no sooner than 21 days after the first infusion. If infusions are suspended after the first, second, or third dose, an MRI is to be performed and reviewed prior to the fourth infusion.  MRI at V4 is to be performed and reviewed prior to V4 infusion.  MRI at V4 may occur 14 days before the scheduled visit date without protocol deviation.

		Part B: Open-Label															Part B: Follow-Up, UV, ED				Comments			
		Visit Number	UP b	1	2	3	4	5	6	7	8	9	10	11 c	12 c	13 c	14 c	15	801 d	802 d	UV	ED		
Weeks Relative to Baseline (V1)		0		4	8	12	16	20	24	28	32	36	40	44	48	60	72	84	96	997			Procedures for some visits may take more than 1 day.	
Visit Interval Tolerance (days)		-		-7 to +10	±7	±7	±7	±7	±7	±7	±7	±7	±7	±7	±7	±7	±7	±7	±7	±7				
Florbetapir F 18 PET scan													X									X e	Florbetapir F 18 PET scan may occur ±14 days from scheduled visit date without protocol deviation.	
Clinician-Administered Assessments (Electronic)																								

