#### **PET Scan Safety**

The primary risk related to florbetapir F 18 PET is radiation exposure. Details on the amount of exposure estimated to occur on each imaging occasion and cumulatively are presented in the tables below and will be provided in the ICF. Details on the clinical information to date regarding florbetapir F 18 exposure will be provided in the ICF. More detailed information about the known and expected benefits and risks of florbetapir F 18 can be found in the US Package Insert for florbetapir F 18 Injection (Amyvid™ package insert, 2012).

Participants must minimize movement during each PET procedure, which can last 20 to 30 minutes for each scan. Most state-of-the-art imaging systems are designed to reduce head motion and participant discomfort.

**PART B:** The table below shows the effective radiation dose of the Study AACH's PET scans.

Effective Dose (mSv) per Scan*	Number of Scans in First Year**	Effective Dose (mSv) for Scans in First Year	Number of Scans in Second Year	Effective Dose (mSv) for Scans in Second Year	Sum of Effective Dose (mSv) for Years 1 and 2	
Florbetapir F 18 Scan (10 mCi IV)	7.43	1	7.43	0	0	7.43
Totals		1	7.43	0	0	7.43

Abbreviations: CT = computed tomography; ED = early discontinuation; IV = intravenous; PET = positron emission tomography.

\*Dose shown includes radiation exposure from the radiotracer and assumes a nonclinical CT scan is obtained (estimated at 0.4 mSv) as part of the PET scan attenuation correction process when the scan is done on a PET/CT scanner. A clinical CT scan is not needed during the PET scan session and, because it will add additional radiation exposure, it is not recommended.

Note: In the event a repeat scan is required (for example., the scan is not analyzable), 1 additional florbetapir F 18 scan may be received. If an ED visit is performed, collect florbetapir F 18 PET scan only if a florbetapir F 18 PET scan has not yet been performed and participant has received at least 3 doses of donanemab.

**PART C:** The table below shows the effective radiation dose of the Study AACH's PET scans.

	Effective Dose (mSv) per Scan*	Number of Scans in Part C	Effective Dose (mSv) for Part C
Flortaucipir F 18 Scan (10 mCi IV)	9.10	1	9.10
Florbetapir F 18 Scan (10 mCi IV)	7.43	1	7.43
Totals		2	16.53

Abbreviations: CT = computed tomography; IV = intravenous; PET = positron emission tomography.

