8.6. Clinical Outcomes

Longitudinal assessment across the feeder study and study AACH will be summarized for Part C participants for ADAS-Cog₁₃, ADCS-iADL, iADRS Total Score, CDR Sum of Boxes, and MMSE Total Score. Change from baseline to each scheduled collection of these measures during the feeder study, to the first on-site assessment from Part A of study AACH, and to the Part C assessment of study AACH will be modelled with an analysis of covariance (ANCOVA) model with factors for baseline score, baseline age, years of education, presence/absence of anti-dementia medications (yes/no), and AACG treatment group.

For comparison purposes to an untreated participant population, change from baseline to each of the same visits will be shown for AACH subjects that participated in Part B of AACH, with the exception that the Part C assessment would be replaced by the Part B Visit 1 (prior to treatment) assessment.

Additionally, each of these outcomes will be analyzed on an annualized basis. Time from the baseline assessment to each post-baseline assessment will be determined and divided by 365 to derive a change per year value. These values will be modelled using the same ANCOVA analysis specified above.

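### The Part B change-from-baseline models leave out the baseline value; if baseline severity drives both dropout and decline, the single-arm Week 72 mean change is modestly biased

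*Protocol*

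**What the plan says.** Protocol 9.4.3 gives three Part B efficacy models.

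- **Clinical scales:** "MMRMs will be fit to the Part B data up to Week 72 for" five named scales, with the terms "The models will include terms for visit, age, years of education, and presence/absence of anti-dementia drugs". Neither the response variable nor the covariance structure is stated. Section 3 defines the endpoint as change from baseline.
- **Amyloid:** "Change from baseline in brain amyloid deposition at Week 36 and Week 72 of Part B will be assessed using an MMRM", with the same terms as the scales.
- **Brain volume:** an ANCOVA of Week 72 change. "The model will include terms for age, years of education, and presence/absence of anti-dementia drugs".

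None includes the baseline score, amyloid level or volume.

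The scales are measured at Visit 1 before dosing; SAP 8.6 relies on this when it says "the Part C assessment would be replaced by the Part B Visit 1 (prior to treatment) assessment". The MRI baseline comes from the originating study or from a scan before Visit 1: "Perform prior to V1 at UP if last recorded MRI from originating study occurred >12 months before V1" (protocol 1.3, Part B). Florbetapir PET is scheduled once in Part B, at Week 36. At early discontinuation, sites are to "collect florbetapir F 18 PET scan only if a florbetapir F 18 PET scan has not yet been performed" (protocol 10.5), and only after at least 3 doses. The radiation table in 10.5 shows 1 scan in year 1 and 0 in year 2.

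SAP 7.5 only summarizes the Part B scales across visits. The SAP's Part C models do use baseline; SAP 8.6 lists "factors for baseline score, baseline age, years of education, presence/absence of anti-dementia medications (yes/no), and AACG treatment group". The protocol's own Part C ANCOVA in 9.4.4 does not.

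**The concern.** Part B has one arm, so the estimate is the mean change itself, and a shift caused by who remains is not cancelled by a control group. A likelihood-based repeated-measures model allows for dropout only through what it contains. If the response is change, with Visit 1 neither a response nor a covariate, dropout that depends on the Visit 1 score is only partly accounted for, through later visits.

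Protocol 9.4.3 also allows progression from these models to be set against expected untreated progression. A shifted mean would go straight into that comparison, and a model without baseline cannot be standardized to the severity of an untreated reference group.

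**Working it through.** **The plan's own figures.** The documents give no power, precision or dropout rate for Part B. The only power figure is for Part A (9.2), and it is not in dispute: simulating it with n = 180, r = 0.80 and SDs 8 and 9 gives an average ICC of 0.793 and an average interval of 0.732 to 0.842, against the stated 0.793 and 0.732 to 0.841.

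**Inputs from the documents.** Baseline ADAS-Cog13 SD 8.5, midway between 8 and 9 (9.2). Six post-baseline visits with scales, at Weeks 12, 24, 36, 48, 60 and 72 (1.3). Overall loss 1 − 150/200 = 25% (9.2), used as a stand-in for Part B.

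**Assumed inputs.** True Week 72 change about 6 points; random-slope SD 6; measurement-error SD 3; slope of true change on true baseline 0 to 0.3 points per point; dropout odds ratio 1 to 2 per baseline SD; 40% loss as a harsher case; 60 to 100 Part B participants. Age, education and anti-dementia drugs were not simulated.

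**Clinical scales.** A single arm was simulated with 30,000 participants, with dropout depending only on observed baseline, and fitted by maximum likelihood with unstructured covariance. Bias in the Week 72 mean change, in points; the two baseline-adjusted columns are evaluated at the mean baseline of all treated participants:

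| Loss | Odds ratio per SD | Slope | Change, no baseline | Baseline main effect | Baseline-by-visit | Raw scores, Visit 1 as response |
|---|---|---|---|---|---|---|
| 25% | 1 | 0 to 0.3 | 0.00 | 0.00 | 0.00 | 0.00 |
| 25% | 2 | 0 | +0.03 | +0.01 | +0.01 | +0.01 |
| 25% | 1.5 | 0.3 | −0.13 | −0.13 | +0.01 | +0.01 |
| 25% | 2 | 0.2 | −0.14 | −0.15 | +0.01 | +0.01 |
| 25% | 2 | 0.3 | −0.22 | −0.23 | +0.01 | +0.01 |
| 40% | 2 | 0.2 | −0.25 | −0.28 | −0.01 | −0.01 |
| 40% | 2 | 0.3 | −0.39 | −0.41 | −0.01 | −0.01 |

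Against a true change of 5.93, the largest biases are 0.22/5.93 = 3.7% at 25% loss and 0.39/5.93 = 6.6% at 40%. A baseline main effect alone removes nothing when the dependence grows over time. Baseline-by-visit evaluated at the average baseline of the observed rows still leaves −0.11 (25% loss, odds ratio 2, slope 0.3).

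**Against sampling error.** The SD of Week 72 change is about √(6² + 3² + 3²) = 7.35, taken as 7.4. At 25% loss the standard error is 7.4/√(0.75 × 60) = 1.10 to 7.4/√(0.75 × 100) = 0.85. At 40% loss it is 7.4/√(0.60 × 60) = 1.23 to 7.4/√(0.60 × 100) = 0.96. Taking the smaller standard error each time, the largest biases are 0.22/0.85 = 0.26 and 0.39/0.96 = 0.41 of a standard error.

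**Single-time-point ANCOVA (volume).** With an intercept, and covariates held at their means among those analysed, the adjusted mean equals the completers' raw mean whatever covariates are added. The bias is the completers' baseline shift times the slope of observed change on observed baseline. At 25% loss and odds ratio 2 the shift is −0.179 SD. On the ADAS-Cog13 scale that is −0.179 × 8.5 = −1.52 points. With error share 9/72.25 = 0.125 and true slope 0.3, the observed slope is 0.3 × 0.875 − 0.125 = 0.1375, and the bias is −1.52 × 0.1375 = −0.21. Simulation gave −0.20 without baseline, −0.20 with baseline at the default adjusted mean, and +0.01 with baseline evaluated at the mean of all treated participants.

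**Amyloid.** Setting 9.4.3 beside the schedule is enough: it plans Weeks 36 and 72, the schedule has one scan around Week 36, and the secondary endpoint names Week 36 only. No Visit 1 scan exists, so the baseline must come from elsewhere, and neither document names the source for Part B.

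**The case against.** The strongest reply is that the clinical response variable is not stated. Section 9.4.3 refers to Part B data for the scales but says change from baseline for amyloid and volume. If raw scores are modelled with Visit 1 as a response under unstructured covariance, the baseline is already in the likelihood and the bias disappears. That stands, and it is why the point is conditional; the text still has to say which model is meant.

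It also stands that Part B has no hypotheses (9.1), its primary objective is safety, and participants who stop treatment remain in follow-up (7.1). SAP 7.5 may mean that the models are no longer planned, although the SAP does not say so.

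A reader might infer four stronger things that the documents do not support.

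- **That the Week 72 result is biased.** This needs baseline to predict both dropout and change, and the documents show neither. A separate simulation with 40% loss and log-odds 1.0 per SD (odds ratio about 2.7) gave 5.3 against a true 6.0, but it pairs a loss above the 25% stated overall with a dependence that nothing in the plan suggests.
- **That the baseline is collected in Part B for all three outcomes.** It is for the scales. It is not for amyloid, and for volume it may be an originating-study scan.
- **That the error always favours donanemab.** With slope 0 the sign reverses (+0.03). For a single-scan outcome, an assumed slope of change on baseline amyloid of −0.8 and a completers' shift of −0.11 to −0.18 SD give +0.09 to +0.14 baseline SD, which understates removal.
- **That Part B is the one exception.** That holds within the SAP only; protocol 9.4.4 also leaves baseline out of its Part C model.

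**Conclusion.** The omission is real in all three Part B models and worth correcting, but its likely effect is modest. If the clinical response is change, the bias in the Week 72 ADAS-Cog13 mean is about 0 to 0.2 points at 25% loss, and about 0.25 to 0.4 at 40% loss with an odds ratio of 2 per SD and slopes of 0.2 to 0.3. Both lie below one standard error. It is zero if dropout is unrelated to baseline, and essentially zero if Visit 1 is modelled as a response. Part B size, Part B loss, the slopes and the odds ratios are all assumptions. The effect is on estimation of secondary endpoints, not on any test.

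For amyloid, the firmer finding is different: the plan analyses a Week 72 change with no scheduled Week 72 scan and does not name the baseline scan.

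**What to change.** 1. **Clinical scales, protocol 9.4.3.** State the response as change from baseline. Add the Visit 1 score and its interaction with visit to each model, and evaluate the adjusted mean at the mean baseline of all dosed participants. Alternatively, model raw scores with Visit 1 as a response under unstructured covariance. State the covariance structure either way.
2. **Volume.** Add the baseline MRI value, defined as the last scan before the first dose (originating study or unscheduled procedure before Visit 1), and evaluate at the mean of all dosed participants. The default adjusted mean would leave the bias in place.
3. **Amyloid.** Name the source of the baseline scan, and reconcile the Week 72 analysis with the schedule and with the Week 36 endpoint.
4. **SAP 7.5.** Carry the models in, or state that the Part B analysis is now descriptive and why.

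The cost is drafting and slightly more analysis work. The SAP has no Part B efficacy model to extend, so one must be written, and the adjusted-mean reference must be programmed because it is not the default. The scale and volume changes need no new data.
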